#### Clinical Laboratory

Clinical laboratory parameters will have observed values and changes from Baseline summarized at each scheduled visit by treatment group.

Values outside the normal range will be categorized as above the normal range (H) or below the normal range (L) based on the laboratory's reference range and these will be flagged in the listings of individual subject data.

#### Vital Signs

Vital sign observed values and changes from Baseline will be summarized at each scheduled visit by treatment group.

#### ECG

The overall ECG interpretation will be summarized by presenting the number and percentage of subjects with "Normal" "Abnormal, not clinically significant", and "Abnormal, clinically significant".

ECG parameters (e.g., QTcF) will have observed values and changes from Baseline summarized at each scheduled visit by treatment group.

#### Physical Examination

Physical examination results will be summarized with incidence of "Normal" and "Abnormal" by body system at each scheduled visit by treatment group.

#### Assessment of Suicidal Ideation and Behavior

Subjects will be assessed for suicidal ideation and behavior using C-SSRS.

The C-SSRS consists of 2 major aspects: Suicidal Ideation and Suicidal Behavior. The following endpoints will be used to analyze C-SSRS data:

- Presence of Suicidal Ideation: Set to 1 if any ideation is present and 0 otherwise,
- Presence of Suicidal Behavior: Set to 1 if any type of suicidal behavior is present and 0 otherwise,
- Suicidal ideation score: Defined as the maximum suicidal ideation category (1-5) present on the C-SSRS at the assessment. A score of 0 is assigned if no ideation is present.

The number (%) of subjects with presence of suicidal ideation and behavior will be summarized at each assessment time. The C-SSRS data will be summarized using worst-case shift from baseline tables.

#### ADA to Tildrakizumab

For each subject, tildrakizumab serum concentrations and ADA sample results are matched to actual sampling times and treatment. Subjects are grouped based on the actual treatment received. The anti-tildrakizumab immunogenicity status of evaluable subjects, along with titer will be summarized by dose level.

#### **12.3.2 Pharmacokinetic Analysis**

Serum tildrakizumab concentration data will be listed by individual subject and summarized by visit. The subjects will be summarized based on the ASaT population with the actual treatment received at a specific visit. All samples for PK and ADA studies will also be saved for future safety or biomarkers analysis as deemed appropriate by Sun Pharmaceuticals. A list of biomarkers is provided in [Appendix 22.3](#).

PK parameters may be used to refine previous PK models.

#### **12.3.3 Interim Analysis**

An IA to review safety data will be performed at one year of this long-term extension study. Additional IAs may be performed as needed to support reporting requirements or as needed for internal decision-making.

#### **12.3.4 Data Safety Monitoring Board**

According to FDA Guideline “Establishment and Operation of Clinical Trial Data Monitoring Committees”, March 2006, a Data Safety Monitoring Board is not required for this extension study.

#### **12.3.5 Clinical Adjudication Committee**

A CAC will evaluate an extensive set of cardiovascular events and all deaths to determine which of these meet pre-specified endpoint criteria. Cardiovascular events for adjudication

will be identified based on Investigator reports with specific AE terms. Instructions for obtaining source documentation for all events to be adjudicated will be provided to the Investigator study sites in a separate document. All personnel involved in the adjudication process will remain blinded to treatment allocation throughout this long-term extension study until such time the study may become open-label. Specific details regarding the cardiovascular endpoints to be analyzed, including the endpoint definitions and criteria can be found in the Adjudication Committee Charter.

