## 9 INVESTIGATIONAL PLAN

### 9.1 Overall Study Design and Plan

#### 9.1.1 Description

This is a long-term extension study of tildrakizumab in subjects with PsA who have previously completed the treatment period of studies with tildrakizumab. Eligible PsA subjects who have previously completed the treatment period of Phase 2b study (CLR\_16\_23) will be entered into this long-term extension study.

The study will be multinational and conducted in approximately 70 study sites. All study sites used in the parent study can enter subjects to this long-term extension study, based on subject eligibility. Up to 286 subjects with PsA could be enrolled from the parent Phase 2 study. Treatment allocation will be based upon the dose regimen assigned at the end of the treatment period in the parent study, with all subjects receiving tildrakizumab in the long-term extension study. All subjects who meet the inclusion criteria and have completed the parent study treatment period (up to Week 48 for the parent Phase 2 study will return for the End of Treatment [EoT] visit at Week 52 of the parent study). The eligible subjects will continue to be administered one of the following dose regimens – 200 mg Q4W, 200 mg Q12W or 100 mg Q12W to maintain the blind of the ongoing parent study to at least Week 52 of the parent study. Thereafter, all subjects began migrating to receive 100 mg tildrakizumab SC injection Q12 weeks in an open-label fashion for up to an additional 4 years provided that they meet clinical response criteria (as defined in [Section 9.3.1](#)).

Note: eligibility for the long-term extension study will be based on response criteria at Week 52 of the parent study [using Week 48 laboratory data from the parent study where relevant for calculations] regardless of timing of subject entry. Subject eligibility for continuation to the long-term extension study based on the clinical response criterion will be determined by the interactive voice response service (IVRS). A flow diagram of the study design is presented in [Figure 9-1](#) below.

The study will consist of a Baseline visit (Week 0) which will be the same as Week 52 of the parent study, 12-weekly visits (from Week 12) up to approximately 2 years from the start of the extension study, followed by 24-weekly visits thereafter (from Week 108) up until approximately 4 years after the start of the study (approximately 5 years from the start of the parent study).

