## Statistical Analysis Plan (SAP)

- 200 mg q12 weeks arm: subjects will receive tildrakizumab 200 mg (two 1-mL injections of 100 mg/mL) at Weeks 8, 20, 32, 44, 56, and all subsequent 12-weekly time points to Week 200, as well as placebo (two 1-mL injections) at interim 4-weekly time points commencing at Baseline of the Phase 2 parent study up to Week 196
- 100 mg q12 weeks arm: subjects will receive tildrakizumab 100 mg (one 1-mL injection of 100 mg/mL + 1 mL placebo) at Weeks 8, 20, 32, 44, 56, and all subsequent 12-weekly time points to Week 200, as well as placebo (two 1-mL injections) at interim 4-weekly time points commencing at Baseline of the Phase 2 parent study up to Week 196

If a subject misses a visit and/or a scheduled dose of IMP, the site must reschedule a visit to ensure the dose of IMP is taken as soon as possible within the visit window. If after 2 attempts to reschedule, the subject still is not able to take the dose, the Sponsor should be contacted to determine if the subject should be discontinued from the study.

Following the last subject's Week 52 visit or early termination prior to Week 52, all subjects will begin migrating to receive 100 mg tildrakizumab SC injection Q12 weeks in an open-label fashion.

A detailed description of procedures and assessments to be conducted during this study is summarized in the Schedule of Assessments in Table 1 below.

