# Statistical Analysis Plan (SAP)

## 8 STATISTICAL METHODS

### 8.1 General Statistical Conventions

All statistical procedures will be completed using SAS version 9.4 or higher.

Continuous variables will be summarized using descriptive statistics, including number of subjects (n), mean, median, standard deviation (SD), minimum and maximum. One additional decimal point for mean and median and 2 additional decimal points for SD will be used.

For categorical variables, summaries will include counts of subjects and percentages. Percentages will be rounded to one decimal place.

Two-sided 95% confidence intervals (CI) will be provided when relevant.

For summary purposes, baseline will be defined as the last available value prior to the date of first IMP administration in parent study.

For reporting purpose, summary tables for efficacy variables and safety variables will be displayed by nominal visit as appropriate. Unscheduled assessments will not be included in the summary tables, but will be in data listings.

All subject data, including those derived, will be presented in individual subject data listings. Unless otherwise stated, unscheduled visit results will be included in date/time chronological order, within patient listings only. All listings will be sorted by treatment group, subject number, date/time and visit. The treatment group as well as patient's sex and age will be stated on each listing. Unless otherwise stated, data listings will be based on ASaT population.

The treatment groups will be displayed in the format below in tables:

- 200 mg Tildrakizumab q4wk
- 200 mg Tildrakizumab q12wk
- 100 mg Tildrakizumab q12wk

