## 8.7 Safety analyses

Safety analyses will be conducted on the ASaT population and will be performed for all safety variables specified below.

The subjects will be summarized based on the actual treatment received at the beginning of the extension study.

The safety analyses of changes from baseline to a specific time point in safety variables (e.g., laboratory parameters, vital signs, and ECG) will only include subjects from ASaT who have data available for both the baseline and the time point under consideration unless otherwise specified. Where relevant, temporal relationships to parent study baseline will be described.

No statistical tests will be performed.

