## **Adverse Events of Special Interest (AESIs)**

The events of severe infections, malignancies (including non-melanoma and melanoma skin cancer, excluding carcinoma in situ of the cervix), confirmed Major Adverse Cardiac Events (MACE), and drug-related hypersensitivity reactions will be identified a priori as AESIs for summarizing in this study. Severe infections are defined as any infection meeting the regulatory definition of a SAE, or any infection requiring IV antibiotics whether or not reported as a serious event, as per the regulatory definition. Major Adverse Cardiac Events include non-fatal stroke, non-fatal myocardial infarction and cardiovascular death. All MACE events will be evaluated and adjudicated by a Clinical Adjudication Committee. The AESIs will be summarized by SOC, PT and treatment group.

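### Protocol 12.3.5 lets the adjudicators' blind to treatment allocation lapse at the open-label switch, while the SAP tabulates confirmed MACE by starting regimen to the end of the study

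*Protocol*

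**What the plan says.** **Adjudication.** Protocol 12.3.5 sets the scope: "A CAC will evaluate an extensive set of cardiovascular events and all deaths to determine which of these meet pre-specified endpoint criteria". It then says that those involved "will remain blinded to treatment allocation throughout this long-term extension study until such time the study may become open-label". The section refers to the charter for endpoint definitions and criteria, and to a separate document for how sites obtain source documents. Protocol 9.1.1 explains what allocation means here: "Treatment allocation will be based upon the dose regimen assigned at the end of the treatment period in the parent study".

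**Tabulation.** SAP 8.7.1 makes confirmed MACE an adverse event of special interest and states: "All MACE events will be evaluated and adjudicated by a Clinical Adjudication Committee". It adds: "The AESIs will be summarized by SOC, PT and treatment group". SAP 8.7 defines the group: "The subjects will be summarized based on the actual treatment received at the beginning of the extension study". SAP 8.1 fixes the columns: "The treatment groups will be displayed in the format below in tables", followed by 200 mg q4wk, 200 mg q12wk and 100 mg q12wk.

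**Timing.** SAP 3.2.2 allows open-label dosing only once every subject has had at least 52 weeks of blinded dosing in the extension. SAP 3.3 says that after the last subject's Week 52 visit, or earlier termination, "all subjects will begin migrating to receive 100 mg tildrakizumab SC injection Q12 weeks in an open-label fashion". The maximum duration is 208 weeks.

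**Passages that differ.** Protocol 12.3.1 groups subjects by the treatment they were on at the time in question, not by the regimen at entry. Protocol 9.1.1 ends the period on parent-study regimens at parent Week 52, which is extension Week 0; SAP 3.1 ends it at extension Week 52.

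**The concern.** The allocation that 12.3.5 protects is the regimen carried in from the parent study, and under the SAP that same regimen defines the table columns through Week 208. The duty to stay blinded ends at the switch, but the use of the classification does not.

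Whether an event is a confirmed MACE, or a death is cardiovascular, is a judgement even with written criteria. An adjudicator who knows that a subject came from the most intensive regimen could be swayed in either direction. The standard of adjudication could also change partway through a table that pools both periods. Long-term safety is the current protocol's primary objective, and the by-regimen display is a planned output.

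**Working it through.** The documents state no figure for the share of follow-up after the switch, so there is none to reproduce.

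**Inputs from the documents**
- Maximum follow-up: 208 weeks (SAP 3.3).
- Blinded extension dosing: at least 52 weeks for every subject, so the switch follows the last subject's Week 52 (SAP 3.2.2, 3.3).
- Study start: about June 2018 (Protocol synopsis).
- Parent database lock: 05 Nov 2019 (Protocol 7.1). This is 74.6 weeks after 1 June 2018.

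**Assumptions**
- Entry is uniform over a span of *s* weeks, from 0 to 74.6, with the parent lock as the outer bound.
- Follow-up is complete, except in the dropout check.

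**Formulas**
- Last entrant: (208 − 52)/208.
- First entrant: (208 − 52 − *s*)/208.
- Average: (208 − 52 − *s*/2)/208.

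| Entry span *s* (weeks) | Last entrant | First entrant | Average |
|---|---|---|---|
| 0 | 75% | 75% | 75% |
| 26 | 75% | 62.5% | 68.8% |
| 52 | 75% | 50% | 62.5% |
| 74.6 | 75% | 39% | 57.1% |

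The average reaches 50% only at a span of 104 weeks. The first entrant falls below 50% once the span exceeds 52 weeks.

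**Dropout.** Take a constant annual dropout *a*, with λ = −ln(1 − *a*)/52 and *b* the blinded weeks, uniform from 52 to 52 + *s*. The post-switch share of subject-time is 1 − mean(1 − e^(−λb))/(1 − e^(−208λ)).
- Span 52 weeks: 57.6% at 10% a year, 52.1% at 20%, and below half above about 23%.
- Span 74.6 weeks: 52.1% at 10% a year, and below half above about 14%.

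**Other possible end dates for the blind**, for a 1 June 2018 entrant:
- Parent lock: (208 − 74.6)/208 = 64%.
- Protocol amendment of 22 July 2020, 111.7 weeks after that date: (208 − 111.7)/208 = 46%.

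**Weight of one event.** If all 286 subjects enrol, split equally across three columns and none drops out (all assumptions), a column holds 286/3 × 4 = 381 subject-years. One event then moves its rate by 100/381 = 0.26 per 100 subject-years. That is what any single event contributes in a column of that size; it does not estimate adjudication bias.

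**The case against.** **Disclosure is permitted, not stated.** A reader might infer that adjudicators will be told the starting regimen. The documents do not say so. After migration everyone receives 100 mg every 12 weeks, so knowing current treatment does not reveal the column. The adjudication package, or some other source, would have to show the earlier regimen. The charter and the source-document instructions are not available and may keep it hidden. This stands, and limits the point to what the text allows.

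**The grouping rule is disputed.** Under Protocol 12.3.1, post-switch events would all fall in the 100 mg group, and adjudicating them unblinded could not favour one starting-regimen column over another. The SAP says that it supersedes the protocol's statistical considerations, but it also promises to identify substantial differences, and its section 10 lists none. The concern therefore holds under the SAP rule. Under the protocol rule a lesser issue remains: the 100 mg column would mix events from both periods, while the 200 mg columns would hold only events from before the switch.

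**The whole study might seem exposed.** Since some passages put every subject on 100 mg from extension Week 0, a reader might infer an exposure of up to 100%. That does not follow: if everyone starts on 100 mg, SAP 8.7 yields one column and there is no between-regimen classification to bias.

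**The consequence is low.** The extension is non-randomised and has no placebo group, power calculation or statistical tests. Pre-specified criteria limit drift in adjudication. Cases come from investigator reports, and investigators are open-label after the switch, so blinding adjudicators protects only part of the chain. All of this is fair and keeps the priority low.

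**Conclusion.** The point stands as a low-consequence gap that is cheap to close. The available documents require blinded adjudication only up to the open-label switch, while the SAP keeps using the starting regimen to classify confirmed MACE afterwards.

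Under SAP 3.2.2 and 3.3, most planned follow-up falls after the switch on average, given full follow-up and the assumed entry spans. A reader might infer that this holds for every subject and under any attrition; the early-entrant and dropout results above show that it does not.

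The effect is possible bias in one descriptive display. No error rate is involved, and the size of any bias cannot be estimated from the documents. The conclusion rests on the SAP grouping rule and on the charter not already maintaining the blind.

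**What to change.** In Protocol 12.3.5 and the charter, replace the clause that ends the blind with a statement that adjudicators remain blinded to both the parent-study regimen and the starting-extension regimen, for all events, to the end of the study. Mask regimen wherever it appears in the adjudication packages. If the charter already requires this, align 12.3.5 with it.

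Separately, reconcile SAP 8.7 with Protocol 12.3.1 on how post-switch events are grouped, and record the outcome in SAP section 10. The passages on when the parent-study regimens end must also be reconciled.

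The adjudication change costs one sentence in each document and a small redaction step, since source records may mention the regimen in more than one place. It reduces the share of follow-up open to unblinded adjudication under the text to 0%. Case reporting by open-label investigators is unchanged.

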### **13 DIRECT ACCESS TO SOURCE DATA/NOTES**

The Investigator/institution shall provide direct access to source data/documents for study-related monitoring, audits, IEC/IRB review and regulatory inspection.

## **14           QUALITY CONTROL AND QUALITY ASSURANCE**

### **14.1       Conduct of the Study**

The designated CRO and Sun Pharma Global FZE shall implement and maintain quality control and quality assurance procedures with written Standard Operating Procedures (SOPs) to ensure that the study is conducted and data are generated, documented and reported in compliance with the protocol, ICH GCP, and applicable regulatory requirements.

This study shall be conducted in accordance with the provisions of the Declaration of Helsinki (October 2013), United States Food and Drug Administration (FDA, Code of Federal Regulations [CFR], Sections 312.50 and 312.56), European Union (Annex 1, Directive 2001/83/EC) and United Kingdom regulations (The Medicines for Human Use [Clinical Trials] Regulations 2004 [No. 1031]), and with ICH GCP (Committee for Proprietary Medicinal Products [CPMP] 135/95).

The Investigator may not deviate from the protocol without a formal protocol amendment having been established and approved by an appropriate IEC/IRB, except when necessary to eliminate immediate hazards to the subject or when the change(s) involve(s) only logistical or administrative aspects of the study. Any deviations may result in the subject having to be withdrawn from the study and render that subject non-evaluable.

### **14.2       Study Monitoring**

The Investigator shall permit the designated CRO site monitor to review study data as frequently as deemed necessary to ensure that data are being recorded in an adequate manner and that protocol adherence is satisfactory.

The Investigator will provide access to medical records for the designated CRO site monitor in order that entries in the eCRF may be verified. The Investigator, as part of his/her responsibilities, is expected to co-operate with the designated CRO in ensuring that the study adheres to GCP requirements.

The Investigator may not recruit subjects into the study until such time that a visit, or with the agreement of the Sponsor, attendance at the Investigator meeting, has been made by a Sponsor/designated CRO site monitor to conduct a detailed review of the protocol and eCRF.

## **15        ETHICS**

### **15.1      Independent Ethics Committee/Institutional Review Board**

Prior to the start of the study, the Investigator is responsible for ensuring that the protocol and ICF have been reviewed and approved by a relevant IEC/IRB. The IEC/IRB shall be appropriately constituted and perform its functions in accordance with FDA, ICH GCP, and local requirements as applicable.

The IEC/IRB shall approve all protocol amendments (except for logistical or administrative changes), written informed consent documents and document updates, subject recruitment procedures (e.g., advertisements), written information to be provided to the subjects, Investigator's Brochure, available safety information, information about payment and compensation available to subjects, the Investigator's curriculum vitae and/or other evidence of qualifications, and any other documents requested by the IEC/IRB and Regulatory Authority (Competent Authority) as applicable.

### **15.2      Written Informed Consent**

The nature and purpose of the study shall be fully explained to each subject (or their legally responsible guardian).

Written informed consent must be obtained from each subject (or guardian) prior to any study procedures being performed. The process of obtaining informed consent must be documented in the subject source documents.

The consent documents to be used for the study shall include all the elements of informed consent as outlined in accordance with FDA, ICH GCP, and local requirements as applicable and be reviewed and approved by the appropriate IEC/IRB prior to use.

### **15.3      Data Safety Monitoring Board**

According to FDA Guideline “Establishment and Operation of Clinical Trial Data Monitoring Committees” , March 2006, a Data Safety Monitoring Board is not required for this extension study.

## **16 DATA HANDLING AND RECORD KEEPING**

### **16.1 Case Report Forms/Source Data Handling**

All required study data must be entered in the eCRF created for the study. This data collection tool is a validated electronic data capture (EDC) system that contains a system generated audit trail. Data required according to this protocol are recorded by investigational study site personnel via data entry into the internet based EDC software system. The Investigator shall ensure that all data from subject visits are promptly entered into the eCRFs in accordance with the specific instructions given. The Investigator must sign each eCRF to verify the integrity of the data recorded. All internal designated CRO and external investigational study site personnel seeking access to the eCRF are supported by a Service Desk (if applicable). At the end of the study all data captured electronically will be provided to the Investigator on CD-ROM for archiving at the investigational study site.

A list of the normal ranges for all laboratory tests to be undertaken forms part of the documentation to be collated prior to study start. It is essential that all samples be analyzed at the central laboratory, unless otherwise specified (e.g., ESR).

The Investigator must maintain source documents, such as laboratory reports, X-rays, ECGs, consultation reports, and complete medical history and physical examination reports. All information in the eCRF must be traceable to the source documents in the subject's file.

